Inclusion criteria: See Aim "A" plus routinely performed blood, urine and respiratory tract specimen sampling

Required tasks for this sub-study:

- Collecting left-over blood samples, urine and respiratory tract samples from routine clinical work-up
- Sampling schedule:
 - o **Blood** (left-over samples only): Plasma and serum at the day of ICU admission, followed by 1 - 3 times per week. Blood samples need to be aliquoted in up to 3 aliquots each containing at least 500 µL.
 - o **Urine:** Sampling at the day of ICU admission, followed by 1 - 3 times per week (on the days of blood sampling). Samples should be divided in aliquots, with a total volume of 10 mL for each visit.
 - o **Respiratory tract samples:** BALF or tracheal aspirate whenever collected during clinical routine. Divide in up to 3 aliquots, each containing at least 1 mL. In case remaining samples volume is less than 1 ml, addition of sterile NaCl 0.9% is necessary to obtain at least one aliquot containing at least 1 mL of respiratory specimen. Highly viscous samples may be diluted with NaCl 0.9% to enable further work up.

Note:

All samples should be stored at -80°C without any pretreatment at the participating center. For low volume respiratory tract samples or highly viscous samples please see above. Don't use liquefying agents such as Sputasol® for this part of the study. For labeling of the samples, see the attachment "*Sample labeling*".

Aim “C”: Microbiota study (ICU patients and patients on general wards)

Aim: Determine diagnostic performance of mycobiome tests in COVID-19 patients

Inclusion criteria: See Aim “A” plus routinely performed BAL or tracheal aspiration in ICU patients OR patients are willing to give sputum samples if they are on general wards after signing an informed consent

Required tasks for this sub-study:

- Collecting BAL or tracheal aspiration in ICU patients and/or sputum samples (once) from patients on general wards

Respiratory sample processing for sub-study “C”:

Respiratory samples will be collected and by heating the samples to 80°C for 40 minutes. A sample volume of at least 0.5 ml is required, but a sample volume of >1mL would be optimal. Samples will then be stored at the participating center and sent to [name] from the University of Manchester in batches on dry ice.

- Also see attachment “COVID-19 Sample Inactivation v5.1””

Sample labeling for biomarker study “B”

All samples collected within this study are supposed to be stored at -80°C at the participating centers and sent to the different labs in batches. We will introduce you where and when to send the samples as required.

Label samples as shown here:

“CenterID_PatientID_Specimen_Day”

CenterID: every participating center will receive a two digit ID that you will receive on the first page of the questionnaire on clinicalsurveys.com

PatientID: patients should be coded by consecutive two digit numbers, starting with 01 for the first included patient at each site

Specimen: should be coded as following:

- Bronchoalveolar lavage fluid = BAL
- Tracheal Aspirate = TA
- Sputum = SP
- Plasma = PL
- Serum = SE
- Urine = UR

Day: indicates the day after the first sample for this study was drawn, with day 0 being the first day where a study sample was drawn and stored (regardless of the specimen).

Examples:

“01_05_BAL_6” = “Graz/AUT_Patient 5 from Graz_Bronchoalveolar lavage fluid_sampled on day 6 after first sample (e.g. urine) was drawn.

“01_05_PL_0” = “Graz/AUT_Patient 5 from Graz_Plasma_sampled on day 0 after first sample (e.g. urine) was drawn – in this case Plasma was the first sample drawn for the study.

## Statistical methods

The primary study analysis was aimed at assessing the impact of posaconazole prophylaxis on the risk of coronavirus disease 2019 (COVID-19)-associated pulmonary aspergillosis (CAPA) in critically ill patients with COVID-19 in intensive care unit (ICU). To this aim, incidence rates (IR) of CAPA in the different centers were first calculated with standard methods, and compared between Graz (all patients undergoing posaconazole prophylaxis) and the other two centers (no patients undergoing posaconazole prophylaxis) for descriptive purposes and unadjusted for confounding factors, by means of the mid-P exact test [1]. Then, to minimize the impact of difference in the case-mix of patients between centers on the risk of CAPA, patients from Graz (i.e., undergoing posaconazole prophylaxis) were matched as a case with controls Genoa and controls from Rennes, according to demographic and relevant clinical variables. Before matching, demographic and clinical characteristics of patients in the three different centers were descriptively compared with the standardized difference (SD) of means and the Wilcoxon test for continuous variables, and with the SD of proportions and the chi-squared test for categorical variables. The SD of means/proportions was also reported for the comparison between cases (i.e., patients from Graz) and controls (i.e., patients from Rennes and Genoa).

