### Matching procedure

#### *1:1 matching*

Each patient from Graz (i.e., undergoing posaconazole prophylaxis) was matched as a case with one control from Genoa and one control from Rennes (i.e., not undergoing posaconazole prophylaxis), employing two separate 1:1 propensity score (PS) matching procedures (one for identifying the control from Genoa and one for identifying the control from Rennes) [2,3]. The following variables were considered for matching cases with controls: (i) age; (ii) sex; (iii) treatment with tocilizumab; (iv) time at risk. We did not match for systemic steroid treatment since all patients from Graz received systemic steroids, thus we consider for possible match only those controls receiving systemic steroids in Genoa and Rennes (i.e., the majority of patients in the two centers). Time at risk was defined as follows: (i) for cases: days on posaconazole prophylaxis plus, if present, days in intensive care unit before posaconazole prophylaxis initiation; (ii) for controls: days in intensive care unit. In order to guarantee equal time at risk in cases and respective controls, we started by matching the case with the longest time at risk (53 days) to possible controls with time at risk equal or longer than 53 days. Then, we selected the case with the second longest time at risk and possible remaining controls with equal or longer time at risk. The procedure was repeated until all cases were matched to one control from Genoa and one control from Rennes. Eventually, for the study analyses, we considered only the period of time at risk in controls (starting from intensive care unit admission) that was equal to the time at risk in the respective case (in order to have an exactly equal time at risk in cases and their respective controls).

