#### Assessment of impact of posaconazole prophylaxis on the risk of CAPA after matching

After 1:1 matching, the risk of CAPA was compared between Graz and the other centers by means of multivariable logistic regression. Besides center, other variables included in the multivariable logistic regression model were: (i) European Organization for Research and Treatment of Cancer/Mycoses Study Group Education and Research Consortium (EORTC/MSGERC) risk factor present at ICU admission; (ii) presence of extracorporeal membrane oxygenation (ECMO). A sensitivity analysis including the same variables was also conducted after 1:1:1 matching.

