**Table 2. Incidence rate and incidence rate ratio of CAPA before matching**

Center	IR	
Graz (posaconazole prophylaxis)	1.69 CAPA/1000 patient-days in ICU	
Rennes (no posaconazole prophylaxis)	4.50 CAPA/1000 patient-days in ICU	
Genoa (no posaconazole prophylaxis)	3.01 CAPA/1000 patient-days in ICU	
Center	IRR (95% CI)*	P*
No prophylaxis (Rennes and Genoa) vs. prophylaxis (Graz, reference)	2.38 (0.87-9.08)	0.0720

CAPA, coronavirus disease 2019 (COVID-19)-associated pulmonary aspergillosis; CI, confidence interval; ICU, intensive care unit; IR, incidence rate, IRR, incidence rate ratio. Calculation of IR were as follows:

$$IR_{Graz} = (4 \text{ CAPA}/2368 \text{ patient-days in ICU}) * 1000 = 1.69 \text{ CAPA}/1000 \text{ patient-days in ICU}$$

$$IR_{Rennes} = (38 \text{ CAPA}/8437 \text{ patient-days in ICU}) * 1000 = 4.50 \text{ CAPA}/1000 \text{ patient-days in ICU}$$

$$IR_{Genoa} = (12 \text{ CAPA}/3989 \text{ patient-days in ICU}) * 1000 = 3.01 \text{ CAPA}/1000 \text{ patient-days in ICU}$$

\* The exact Poisson method was employed for calculating 95% CI. The P-value is from exact mid-P test.

Overall, 4, 38, and 12 cases of CAPA were registered in Graz, Rennes, and Genoa, respectively. The distribution of proven, probable, and possible CAPA in the different centers was as follows: Graz (n = 0 proven, n = 3 probable, n = 1 possible); Rennes (n = 0 proven, n = 19 probable, n = 19 possible); Genoa (n = 0 proven, n = 12 probable, n = 0 possible).

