**Table 5. Multivariable logistic regression of factors associated with development of CAPA after 1:1 matching**

Variables	OR (95% CI)	P
EORTC/MSGERC risk factor present at ICU admission	4.35 (1.15-16.49)	0.031
ECMO	1.85 (0.34-9.99)	0.475
Center		0.007
Rennes (vs. Graz as reference)	6.07 (1.76-20.91)	0.004
Genoa (vs. Graz as reference)	0.59 (0.10-3.53)	0.566

CI, confidence interval; CAPA, coronavirus disease 2019 (COVID-19)-associated pulmonary aspergillosis; ECMO, extracorporeal membrane oxygenation; EORTC, European Organization for Research and Treatment of Cancer; ICU, intensive care unit; IQR, interquartile range; MSGERC, Mycoses Study Group Education and Research Consortium; OR, odds ratio.

Overall, 4, 17, and 2 cases of CAPA were registered in Graz, Rennes, and Genoa, respectively, after 1:1 matching. The distribution of proven, probable, and possible CAPA in the different centers was as follows: Graz (n = 0 proven, n = 3 probable, n = 1 possible); Rennes (n = 0 proven, n = 10 probable, n = 7 possible); Genoa (n = 0 proven, n = 2 probable, n = 0 possible).

[figure not shown]
**Table 6 (sensitivity analysis). Multivariable logistic regression of factors associated with development of CAPA after 1:1:1 matching**

Variables	OR (95% CI)	P
EORTC/MSGERC risk factor present at ICU admission	2.84 (0.70-11.63)	0.146
ECMO	1.48 (0.29-7.50)	0.639
Center		0.002
Rennes (vs. Graz as reference)	5.10 (1.54-16.90)	0.008
Genoa (vs. Graz as reference)	0.80 (0.17-3.80)	0.776

CI, confidence interval; CAPA, coronavirus disease 2019 (COVID-19)-associated pulmonary aspergillosis; ECMO, extracorporeal membrane oxygenation; EORTC, European Organization for Research and Treatment of Cancer; ICU, intensive care unit; IQR, interquartile range; MSGERC, Mycoses Study Group Education and Research Consortium; OR, odds ratio.

[figure not shown]
Overall, 4, 16, and 3 cases of CAPA were registered in Graz, Rennes, and Genoa, respectively, after 1:1:1 matching. The distribution of proven, probable, and possible CAPA in the different centers was as follows: Graz (n = 0 proven, n = 3 probable, n = 1 possible); Rennes (n = 0 proven, n = 9 probable, n = 7 possible); Genoa (n = 0 proven, n = 3 probable, n = 0 possible).

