**Figure 1. Flow-chart of the patient selection process**

[figure not shown]
**Figure 1 legend.** Matched cohorts after 1:1 and 1:1:1 matching were both composed of 249 patients, although some different controls could have been selected (for details, see matching methods). COVID-19, coronavirus disease 2019.

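### Prophylaxis is the same variable as centre, so the Table 5 and 6 contrasts measure centre differences and cannot be attributed to posaconazole; the two centres without it differ by as much or more

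*SAP*

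**What the plan says.** The SAP (Statistical methods) gives the primary aim as the impact of posaconazole prophylaxis on CAPA risk. Unadjusted incidence rates are "compared between Graz (all patients undergoing posaconazole prophylaxis) and the other two centers (no patients undergoing posaconazole prophylaxis". Table 2 turns this into one incidence rate ratio, labelled "No prophylaxis (Rennes and Genoa) vs. prophylaxis (Graz, reference", with an exact Poisson interval and a mid-P test. The text calls that comparison descriptive and unadjusted.

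Matching leaves the allocation unchanged: "Each patient from Graz (i.e., undergoing posaconazole prophylaxis) was matched as a case with one control from Genoa and one control from Rennes". Table 3 confirms 83/83, 0/83 and 0/83 on prophylaxis.

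The section headed as the assessment of posaconazole's impact after matching then states that "the risk of CAPA was compared between Graz and the other centers by means of multivariable logistic regression". The model holds centre (three levels), EORTC/MSGERC risk factor and ECMO. Tables 5 and 6 print Rennes against Graz and Genoa against Graz. Rennes against Genoa is not printed. I found no term for variation between centres, and no statement that centre and prophylaxis cannot be told apart.

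**The concern.** With one exposed centre and two unexposed ones, every difference between Graz and a comparator (case mix beyond the matching variables, diagnostic work-up, case classification, local Aspergillus exposure) is carried by the same coefficient as prophylaxis. Patient-level standard errors describe how precisely this centre differs from that one. They say nothing about how far two centres would differ if neither used posaconazole.

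The result at stake is Rennes against Graz: OR 6.07, P 0.004 (Table 5) and OR 5.10, P 0.008 (Table 6). Under a heading about posaconazole's impact, it is easily taken as evidence for the drug. The matched data contain a direct check, the gap between the two centres that both lack prophylaxis, and that gap is not reported.

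**Working it through.** **Inputs.** Table 2: CAPA 4, 38 and 12 over 2368, 8437 and 3989 patient-days (Graz, Rennes, Genoa). Notes to Tables 5 and 6: CAPA among 83 per centre of 4, 17, 2 (1:1) and 4, 16, 3 (1:1:1); probable CAPA 3, 10, 2 and 3, 9, 3.

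**Step 1: reproduce the printed figures.** Pooled controls: 50/12426 patient-days; Graz: 4/2368. IRR = (50/12426)/(4/2368) = 2.38. The conditional-binomial exact interval is 0.87 to 9.08 and the mid-P value 0.0720, as printed. For Table 5, Rennes against Graz, SE = ln(20.91/1.76)/3.92 = 0.631, giving P = 0.0043 (printed 0.004). For Table 6, SE = ln(16.90/1.54)/3.92 = 0.611, giving P = 0.0077 (printed 0.008). The IRR interval uses only counts and patient-days, and the ORs behave as ordinary Wald results.

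**Step 2: the missing contrast, Rennes against Genoa.** Crude OR = a(83−b)/[b(83−a)], SE = √(1/a + 1/(83−a) + 1/b + 1/(83−b)).

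- 1:1: (17×81)/(2×66) = 10.4, SE 0.766, 95% CI 2.3 to 46.8
- 1:1:1: (16×80)/(3×67) = 6.4, SE 0.651, 95% CI 1.8 to 22.8
- 1:1, probable only: (10×81)/(2×73) = 5.5, SE 0.791, 95% CI 1.2 to 26
- 1:1:1, probable only: (9×80)/(3×74) = 3.2, SE 0.686, 95% CI 0.85 to 12.4

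The adjusted values follow from the printed ORs: 6.07/0.59 = 10.3 and 5.10/0.80 = 6.4. Their intervals need a covariance that the SAP does not print.

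| Contrast | 1:1 | 1:1:1 |
|---|---|---|
| Rennes vs Graz, adjusted (Tables 5, 6) | 6.07 | 5.10 |
| Genoa vs Graz, adjusted (Tables 5, 6) | 0.59 | 0.80 |
| Rennes vs Genoa, adjusted (ratio) | 10.3 | 6.4 |
| Rennes vs Graz, crude | 5.1 | 4.7 |
| Rennes vs Genoa, crude | 10.4 | 6.4 |
| Rennes vs Graz, probable only, crude | 3.7 | 3.2 |
| Rennes vs Genoa, probable only, crude | 5.5 | 3.2 |

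The gap between the two unexposed centres exceeds the Rennes–Graz gap in every comparison but one. For probable CAPA in the 1:1:1 set they are equal, because Graz and Genoa both have 3/83.

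**Step 3: how much between-centre variation would matter.** Give each centre its own random shift in log-odds with SD τ (an assumption). The variance of Rennes against Graz, read as a prophylaxis effect, becomes SE² + 2τ². Significance at 5% is lost when τ² exceeds [(ln OR/1.96)² − SE²]/2.

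- Table 5: [(1.803/1.96)² − 0.631²]/2 = 0.224, so τ = 0.47
- Table 6: [(1.629/1.96)² − 0.611²]/2 = 0.159, so τ = 0.40

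A moment estimate from the two unexposed centres, τ² = (d² − v)/2, where d is their crude log OR and v its variance, gives τ = 1.57 (1:1) and 1.23 (1:1:1), or 1.07 and 0.68 for probable CAPA only. With two centres these are very imprecise. They show only that 0.40 to 0.47 is not an extreme assumption.

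**Step 4: Table 2.** On the printed rates, Rennes against Genoa is 4.50/3.01 = 1.50 (exact 95% CI 0.77 to 3.15), and τ is 0.16. For Graz against the mean of the two control log rates, the patient-level variance is 1/4 + (1/38 + 1/12)/4 = 0.277, SE 0.53. Adding 1.5τ² = 1.5×0.0267 gives SE 0.56, which is little change.

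**The case against.** Much can be said for the SAP. Tables 5 and 6 label their rows as centre contrasts, and the intervals are valid for those. Genoa's 0.59 stands directly below Rennes' 6.07 and the event counts are given, so an attentive reader can see the disagreement. The SAP does not say in words that P 0.004 is evidence for posaconazole. All of this stands, and it narrows the point to the section heading, the stated aim and the missing benchmark.

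The 10.4 is also the largest available figure and rests on two Genoa events. Part of the gap follows case classification: possible CAPA is 7 of 17 in Rennes and 0 of 2 in Genoa. That stands too, which is why the probable-only values belong beside it; the 1:1:1 value has an interval that includes 1.

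A reader might go further and infer that every interval in the SAP is far too narrow. The documents do not support that. The EORTC/MSGERC and ECMO odds ratios and the log-rank tests do not estimate prophylaxis. The only printed interval for prophylaxis against none, in Table 2, is called descriptive, already includes 1 and barely widens on its printed rates. Those rates do need reconciling with Table 1: Rennes has 8437/192 = 43.9 days per patient against a median stay of 14 (IQR 10-27), and Genoa 3989/239 = 16.7 against 21 (12-42). That is a separate matter and does not license a stronger claim here.

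One could also build an equal-weight controls-against-Graz OR and widen its 1:1 interval from 0.45–5.5 to about 0.03–83. The SAP prints no such estimate, and that width comes from a variance resting on two centres.

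**Conclusion.** The point holds as one of identification. Exposure equals centre, so the matched analysis cannot separate posaconazole from other centre effects, and no random-effects or cluster-robust variance with three centres repairs that. The Table 5 and 6 intervals are sound for centre against centre. Read as a prophylaxis effect they omit between-centre variation, and the SAP's own unexposed centres differ by a crude OR of 10.4 (1:1) or 6.4 (1:1:1), and by 5.5 or 3.2 for probable CAPA only.

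The two contrasts with Graz also point in opposite directions. A conclusion for posaconazole drawn from OR 6.07, P 0.004 would therefore be unsound. Nor do the data show that posaconazole has no effect: that inference fails for the same reason.

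The counts and odds ratios come from the documents. The thresholds of 0.47 and 0.40 depend on the assumed model of independent centre shifts.

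**What to change.** 1. Add Rennes against Genoa, with its interval, to Tables 5 and 6 (same model, changed reference centre) as the benchmark for variation without prophylaxis, and give a version restricted to probable CAPA.
2. Retitle the post-matching section and Tables 5 and 6 as centre contrasts whose intervals exclude between-centre variance. State that centre and prophylaxis are inseparable in this design, and do not present P 0.004 or 0.008 as evidence for posaconazole.
3. Put the same caveat on the Table 2 IRR.

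An interval computed over a range of assumed between-centre SDs may be added as an illustration, but it is not a correction.

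The cost is one refitted reference level, one restricted rerun and some table wording, with no new data. The price is that the primary result reads less favourably.

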### Matching procedure

#### *1:1 matching*

Each patient from Graz (i.e., undergoing posaconazole prophylaxis) was matched as a case with one control from Genoa and one control from Rennes (i.e., not undergoing posaconazole prophylaxis), employing two separate 1:1 propensity score (PS) matching procedures (one for identifying the control from Genoa and one for identifying the control from Rennes) [2,3]. The following variables were considered for matching cases with controls: (i) age; (ii) sex; (iii) treatment with tocilizumab; (iv) time at risk. We did not match for systemic steroid treatment since all patients from Graz received systemic steroids, thus we consider for possible match only those controls receiving systemic steroids in Genoa and Rennes (i.e., the majority of patients in the two centers). Time at risk was defined as follows: (i) for cases: days on posaconazole prophylaxis plus, if present, days in intensive care unit before posaconazole prophylaxis initiation; (ii) for controls: days in intensive care unit. In order to guarantee equal time at risk in cases and respective controls, we started by matching the case with the longest time at risk (53 days) to possible controls with time at risk equal or longer than 53 days. Then, we selected the case with the second longest time at risk and possible remaining controls with equal or longer time at risk. The procedure was repeated until all cases were matched to one control from Genoa and one control from Rennes. Eventually, for the study analyses, we considered only the period of time at risk in controls (starting from intensive care unit admission) that was equal to the time at risk in the respective case (in order to have an exactly equal time at risk in cases and their respective controls).

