#### Secondary analyses

To assess the prognostic impact of CAPA, 90-day survival in patients with and without CAPA after 1:1 matching was presented graphically using Kaplan-Meier curves, and compared with the log-rank test. To partly avoid immortal time bias, Kaplan-Meier curves were built as landmark analyses with different time of origin (15, 30, and 45 days after ICU admission) including patients still on follow-up at the selected time of origin, and excluding patients developing CAPA after the selected time of origin. It should be acknowledged that residual immortal time bias was present in patients from Genoa and Rennes in this secondary analysis, owing to their matching for time at risk (for the development of CAPA) in the primary study analysis (i.e., patients from Genoa and Rennes always remained alive for at least the time at risk of their respective case from Graz in the primary analysis). A sensitivity survival analysis was also conducted after 1:1:1 matching.

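### Graz cases are identified by receiving posaconazole, but their time at risk includes ICU days before the first dose, so the primary CAPA comparison may carry immortal time bias favouring posaconazole

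*SAP*

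**What the plan says.** The SAP's introductory text under Statistical methods describes the exposed group as "Graz (all patients undergoing posaconazole prophylaxis", against two centers where nobody received it. The 1:1 matching section labels each Graz patient a case on that basis and sets the case's time at risk as "days on posaconazole prophylaxis plus, if present, days in intensive care unit before posaconazole prophylaxis initiation".

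For controls, "we considered only the period of time at risk in controls (starting from intensive care unit admission"), cut to the same number of days as the matched case. The 1:1:1 matching uses the same time at risk.

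After matching, "the risk of CAPA was compared between Graz and the other centers by means of multivariable logistic regression", adjusted for EORTC/MSGERC risk factor and ECMO. The model has no time-dependent exposure term.

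Immortal time is raised once, under Secondary analyses, for 90-day survival: "It should be acknowledged that residual immortal time bias was present in patients from Genoa and Rennes in this secondary analysis". The sections on the primary CAPA comparison do not mention it.

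**The concern.** Exposure is fixed by something that happens after the clock starts. To become a prophylaxis case, a patient has to reach the first dose, ordinarily without diagnosed CAPA. Any ICU days before that dose are unexposed, yet they are credited to the posaconazole group and are likely to contain few or no events.

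The control window also opens at ICU admission, but the text available does not require a control to be CAPA-free on the ICU day when its case started. A control diagnosed in the first days counts as an event. A Graz patient diagnosed on the same day, before any dose, might not have been entered as a case.

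A difference of this kind would raise the control risk relative to Graz, in the direction of the study hypothesis and in the primary comparison. With only four CAPA cases in Graz, a few patients handled differently can move the estimate noticeably. The 1:1:1 analysis cannot reveal the problem, because it uses the same time origin.

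**Working it through.** **Inputs.** CAPA before matching: Graz 4, Rennes 38, Genoa 12, over 2368, 8437 and 3989 patient-days (Table 2). CAPA after 1:1 matching: 4, 17 and 2, with 83 patients per center (notes to Table 5). After 1:1:1 matching: 4, 16 and 3 (notes to Table 6). Matched time at risk: median 15 days, IQR 10-23 (Table 3). Not given: days from ICU admission to first dose, and CAPA onset days.

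**The plan's own figures.** Table 2: (50/12426)/(4/2368) = 2.38, exact 95% CI 0.87-9.08, mid-P 0.0720. This matches the SAP. The adjusted odds ratios in Table 5 (Rennes 6.07, Genoa 0.59) need patient-level data. The crude ones agree with them in direction:
- Rennes vs Graz: (17/66)/(4/79) = 5.09 (Wald 95% CI 1.63-15.86; Fisher P 0.004).
- Genoa vs Graz: (2/81)/(4/79) = 0.49 (0.09-2.74).

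**Expected early control events.** Assumptions: a delay of d days in every case, a constant hazard, and a mean window of 16 days, from (10+15+23)/3. The expected number of Rennes events falling before the case's first dose is 17 × d/16, which is 1.1, 2.1, 3.2 and 4.3 for d = 1, 2, 3 and 4. For Genoa it is 2 × d/16, or 0.1 to 0.5.

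**Effect of removing k such Rennes controls.** OR = ((17−k)/66)/(4/79).

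| k | OR | Fisher P |
|---|---|---|
| 0 | 5.09 | 0.004 |
| 1 | 4.79 | 0.004 |
| 2 | 4.49 | 0.007 |
| 3 | 4.19 | 0.012 |
| 4 | 3.89 (Wald 95% CI 1.21-12.50) | 0.020 |
| 6 | 3.29 | 0.056 |

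The last row lies outside the assumed range. At constant hazard, six events need a delay of 6 × 16/17 = 5.6 days. A hazard concentrated early in the stay would need less.

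A full re-match would draw replacement controls. If each removed control were replaced by one without CAPA, keeping 83 in the arm, k = 1 to 4 gives 4.72, 4.36, 4.01 and 3.67 (P 0.038 at k = 4).

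**1:1:1 set.** Crude (16/67)/(4/79) = 4.72. The expected number of early events is 16 × d/16 = d. Removing 1 to 4 gives ((16−k)/67)/(4/79) = 4.42, 4.13, 3.83 and 3.54 (P 0.035 at k = 4).

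**The other route to the same bias.** Suppose m Graz patients had CAPA before the first dose and were not entered. Adding them to Graz gives (17/66)/((4+m)/79) = 4.07, 3.39, 2.91 and 2.54 for m = 1 to 4 (Fisher P 0.006, 0.014, 0.027 and 0.051). The documents do not say whether there were any such patients.

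**The case against.** The strongest reply is that the bias depends on a rule the documents do not state. A reader might infer that CAPA before the first dose cannot count against a Graz case, that those days are event-free by construction, or that CAPA present at admission was counted only in the control arms. None of these is written in the text available:

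- The SAP calls the pre-dose days time at risk and gives no onset dates for the four Graz cases of CAPA.
- The parent protocol stores respiratory samples, including those from ICU admission, for later biomarker testing. CAPA could therefore be dated before the first dose in a patient already on prophylaxis.
- The flow chart in Figure 1 and the SAP pages before the index could not be read for this check, and may contain a selection rule.
- If the 83 are all eligible Graz ICU patients, with none dropped for early CAPA, ICU admission is a sound common time origin and this bias disappears.
- The SAP says pre-dose days are counted only if present, so the delay may be zero for many patients.

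All of this stands, and it limits what can be claimed about size and certainty. It does not remove the misalignment: exposure is fixed by a later event, the clock starts earlier, and no handling rule is visible.

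**Conclusion.** The concern holds as a possible bias in the primary comparison, not as a demonstrated one. Case status depends on starting posaconazole while time at risk can begin before it, and the text available does not apply a matching CAPA-free condition to controls. Any resulting bias would favour posaconazole.

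Under the assumptions of a 1 to 4 day delay, constant hazard and a 16-day mean window, the Rennes contrast weakens but stays significant. It would be lost only with longer delays, an early-peaking hazard, or about four unentered Graz patients with CAPA.

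It would be wrong to infer that the bias accounts for the findings. Genoa had fewer events than Graz (adjusted odds ratio 0.59 in Table 5, 0.80 in Table 6), which already runs against a benefit. At constant hazard, at most about half a Genoa event would be affected.

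**What to change.** Report three things:
1. The distribution of days from ICU admission to the first posaconazole dose.
2. The number of Graz patients not entered because CAPA was diagnosed before the first dose, or a statement that there were none.
3. For each arm, the number of CAPA events dated before the case's start day.

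Then refit Tables 5 and 6, at least as a sensitivity analysis. Put time zero at the case's start day and at the same ICU day in its two controls. Require all three to be in the ICU and free of CAPA on that day, and count events only from then. Two alternatives would also meet the concern: analyse all eligible Graz ICU patients from admission, or treat posaconazole as a time-dependent exposure.

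The pre-dose days were needed to build time at risk, so this should take a change of SAP wording and a rerun of matching and models on data already held. The cost is a few lost events and slightly wider intervals. The estimate also becomes risk after the start of prophylaxis rather than over the whole ICU stay, and the report should say so. If the delays prove to be near zero and no Graz patient was left out, stating that would settle the point.
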